8.1.1 Cardiovascular Events

Cardiovascular AEs have been seen in subjects receiving trametinib, dabrafenib or both in combination. Guidelines for prolonged QTc interval, LVEF decreases, and hypertension are provided in Section 8.1.1.1, Section 8.1.1.2 and Section 8.1.1.3, respectively.

8.1.1.1 QTc Prolongation

Guidelines for dose modification and stopping criteria due to the QTc prolongation are provided in Table 12.

Table 12 Withholding and Stopping Criteria for QTc Prolongation

QTc Prolongation ¹	Action and Dose Modification

 QTcB ≥501 msec 	
 Interrupt treatment with trametinib and dabrafenib until QTc prolongation resolves to Grade 1 or baseline Test serum potassium, calcium, phosphorus and magnesium. If abnormal, correct per routine clinical practice to within normal limits. Review concomitant medication usage for agents that prolong QTc. If event resolves, restart trametinib and dabrafenib at current dose level² If event does not resolve, permanently discontinue study treatments. Consider evaluation with cardiologist. If event recurs, permanently discontinue trametinib and dabrafenib. Consider evaluation with cardiologist.

Abbreviations: ECG, electrocardiogram; msec, milliseconds; QTc, corrected QT interval; QTcB, QT interval on ECG corrected using the Bazett's formula

- Based on average QTc value of triplicate ECGs. For example, if an ECG demonstrates a prolonged QT interval, obtain 2 or more ECGs over a brief period, and then use the averaged QTc values of the 3 ECGs to determine if trametinib **and** dabrafenib should be interrupted or discontinued.
- If the QTc prolongation resolves to Grade 1 or baseline, the subject may resume treatment with trametinib **and** dabrafenib if the investigator and Medical Lead agree that the subject will benefit from further treatment.

8.1.1.2 Left Ventricular Ejection Fraction (LVEF) Stopping Criteria

Decreases of the LVEF have been observed in subjects receiving trametinib monotherapy and in combination with dabrafenib. Therefore, ECHOs must be performed to assess cardiac ejection fraction at regular intervals as outlined in the Time and Events Table (Section 7.1).

Echo assessment should be performed by the same operator throughout the study where possible. Copies of all ECHOs will be collected by the sponsor for review. Instructions for submission of ECHOs are provided in the SPM. Dose modification guidance and stopping criteria for LVEF decrease are provided in Table 13.

Table 13 Dose Modification Guidelines and Stopping Criteria for LVEF Decreases

Presentation	LVEF decrease (%) or CTCAE Grade	Action and Dose Modification
Asymptomatic	Absolute decrease of >10% in LVEF compared to baseline and ejection fraction below the institutional LLN	
 ● Interrupt study treatment and repeat ECHO within 2 weeks¹ ● Report as an AE If the LVEF recovers within 4 weeks (defined as LVEF ≥LLN and absolute decrease ≤10% compared to baseline) 
 ● Consult with the Medical Lead and request approval for restart ● Restart treatment with trametinib reduced dose by one dose level 
 ● Restart dabrafenib at previous dose level ● Repeat ECHO 2 , 4 , 8 and 12 weeks after re-start; continue in intervals of 12 weeks thereafter ● If LVEF does not recover within 4 weeks 
 ● Consult with cardiologist ● Permanently discontinue study treatment ● Repeat ECHO after 2, 4, 8, 12, and 16 weeks or until resolution 
 ● Consult with the Medical Lead
Symptomatic ²	Grade 3: resting LVEF 39 to 20% or >20% absolute reduction from baseline	
 ● Permanently discontinue study treatment ● Report as a SAE ● Consult with cardiologist
	Grade 4: resting LVEF <20%	
 ● Repeat ECHO after 2, 4, 8, 12, and 16 weeks or until resolution².

Abbreviations: AE, adverse event; CTCAE, Common Toxicity Criteria for Adverse Events; ECHO, echocardiogram; LLN, lower limit of normal; LVEF, left ventricular ejection fraction; SAE, serious adverse event

1. If ECHO does not show LVEF recovery after 2 weeks, repeat ECHO 2 weeks later.

2. Symptoms may include: dyspnea, orthopnea, and other signs and symptoms of pulmonary congestion and edema.

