Subjects should be instructed on the importance of immediately reporting febrile episodes. Therapy with dabrafenib should be interrupted if the patient's temperature is $\geq 38.5^{\circ}\text{C}$ or 101.3°F but trametinib should be continued at the same dose. In the event of a fever, the subject should be instructed to take anti-pyretics (i.e., ibuprofen or acetaminophen/paracetamol) as appropriate to control fever. The use of oral corticosteroids should be considered in those instances in which anti-pyretics are insufficient. Monitor serum creatinine and other evidence of renal function during and following severe events of pyrexia. (See Section 8.2.3 for additional details.)

Decreased left ventricular ejection fraction (LVEF): Left ventricular dysfunction has been reported with trametinib as well as with other MEKi in clinical development. In the 2 Phase III studies decreased ejection fraction occurred in 7% of subjects receiving combination therapy and the majority of the LVEF decreases that met interruption criteria were asymptomatic and resolved. Most subjects who were re-challenged were able to continue on treatment without further dose modification. Subjects enrolled in studies with dabrafenib in combination with trametinib undergo regular cardiac assessments with echocardiograms

(ECHOs). Guidelines for clinical management of treatment-related LVEF decreases have been provided in Section 8.1.1.2.

Hemorrhage: Hemorrhagic events, including major hemorrhagic events defined as symptomatic bleeding in a critical area or organ, and fatal intracranial hemorrhages, have occurred in patients taking dabrafenib in combination with trametinib. The majority of bleeding events were mild. Three of 209 subjects (1%) receiving trametinib in combination with dabrafenib in a phase III trial had fatal intracranial hemorrhagic events. The management of hemorrhagic events may require treatment interruption, dose reduction, or treatment discontinuation.

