g. All events of possible treatment-induced liver injury with hyperbilirubinemia defined as:

- ALT ≥ 5 times ULN and bilirubin ≥ 3 times ULN (>35% direct) or ALT ≥ 5 times ULN and INR >1.5, if INR is measured, with no existing liver disease
OR
- ALT ≥ 8 times ULN **and** bilirubin ≥ 5 times ULN (>35% direct) or INR >1.5, if INR is measured, with pre-existing liver disease

NOTE: INR measurement is not required and the threshold value stated will not apply to subjects receiving anticoagulants.

NOTE: Bilirubin fractionation is performed if testing is available. If testing is unavailable, record presence of detectable urinary bilirubin on dipstick indicating direct bilirubin elevations and suggesting liver injury. If testing is unavailable and a subject meets the criterion of total bilirubin ≥ 3 times ULN, if no existing liver disease or ≥ 3 times ULN if pre-existing liver disease; the event is still reported as an SAE. If INR is obtained, include values on the SAE form. Elevations in INR >1.5 suggest severe liver injury.

h. Protocol-specific SAEs:

- cuSCC (Section 8.2.2.1), new primary melanomas (Section 8.2.2.2) and **non-cutaneous malignancies (Section 8.2.2.3)** with the exception of basal cell carcinoma (BCC). BCC should be reported as an AE or SAE based on the discretion of the investigator.
- LVEF that meets the dose interruption criteria (Section 8.1.1.2): absolute LVEF decreases of $>10\%$ from baseline (not relative decrease) and below the LLN
- Liver chemistry events of ALT $\geq 3 \times$ ULN **and** bilirubin $\geq 2 \times$ ULN ($>35\%$ direct bilirubin) or ALT $\geq 3 \times$ ULN **and** INR >1.5 , if INR measured which may indicate severe liver injury (possible ‘Hy’s Law’) (Section 8.1.3.1)
- RPED also referred to as central serous retinopathy (CSR) or RVO (Section 8.2.7)
- Pyrexia accompanied by hypotension or dehydration requiring IV fluids or renal insufficiency or severe rigors/chills in the absence of an obvious infectious cause (Section 8.2.3).

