11.12 Prompt Reporting of SAEs to Sponsor

Once the investigator determines that an event meets the protocol definition of an SAE, the SAE will be reported to the sponsor within 24 hours. Any follow-up information on a previously reported SAE will also be reported to the sponsor within 24 hours.

If the investigator does not have all information regarding an SAE, he/she will not wait to receive additional information before notifying the sponsor of the event and completing the appropriate data collection tool. The investigator will always provide an assessment of causality at the time of the initial report as described in Section [11.10.2](#), Assessment of Causality.

The primary mechanism for reporting SAEs to the sponsor will be the electronic data collection tool. If the electronic system is unavailable for greater than 24 hrs, the site will use the paper SAE data collection tool and fax it to the Medical Lead. Then the site will enter the SAE data into the electronic system as soon as it becomes available. After the study is completed at a given site, the electronic data collection tool (e.g., InForm system) will be taken off-line to prevent the entry of new data or changes to existing data. If a site receives a report of a new SAE from a study participant or receives updated data on a previously

reported SAE after the electronic data collection tool has been taken off-line, the site can report this information on a paper SAE form or to their sponsor protocol contact by telephone. The sponsor contacts for SAE receipt can be found at the beginning of this protocol on the Sponsor/Medical Lead Contact Information page.

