2.7.1 Adverse events (AEs)

Adverse events (AEs) will be graded according to the CTCAE, Version 4.0. Adverse events will be coded using the Medical Dictionary for Regulatory Activities (MedDRA). For the final analysis, version 24.1 of MedDRA will be used.

All AEs will be summarized based on frequency and proportion of total subjects experiencing the event, grouped by system organ class and preferred term (PT).

A summary of number and percentage of subjects with any adverse events by maximum grade will be produced for each histologic cohort. In this summary AEs will be sorted by PT in descending order of total incidence. The summary will use the following algorithms for counting the subject:

Preferred term row: Subjects experiencing the same AE preferred term several times with different grades will only be counted once with the maximum grade.

Any event row: Each subject with at least one adverse event will be counted only once at the maximum grade no matter how many events they have.

For the legal requirements of ClinicalTrials.gov and EudraCT, two required tables of on-therapy adverse events which are not serious adverse events with an incidence of at least 5% and on-therapy serious adverse events and SAEs suspected to be related to study treatment will be provided by system organ class and preferred term for the all treated subjects population.

If for the same patient, several consecutive AEs (irrespective of study treatment causality, seriousness and severity) occurred with the same SOC and PT:

- a single occurrence will be counted if there is ≤ 1 day gap between the end date of the preceding AE and the start date of the consecutive AE
- more than one occurrence will be counted if there is > 1 day gap between the end date of the preceding AE and the start date of the consecutive AE

For occurrence, the presence of at least one SAE / SAE suspected to be related to study treatment / non SAE has to be checked in a block e.g., among AEs in a ≤ 1 day gap block, if at least one SAE is occurring, then one occurrence is calculated for that SAE.

The number of deaths resulting from SAEs suspected to be related to study treatment and SAEs irrespective of study treatment relationship will be provided by SOC and PT.

All SAEs and fatal SAEs will be tabulated based on the number and percentage of subjects who experienced the event. The summary tables will be displayed in descending order of total incidence by PT only.

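### The protocol gives an asymptomatic, interruption-level LVEF fall two reporting classes: AE in Table 13 and SAE in Section 11.2h

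*Protocol*

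**What the plan says.** Table 13 in Protocol Section 8.1.1.2 sorts LVEF falls by presentation. The asymptomatic row requires an absolute fall of more than 10% from baseline and a value below the institutional LLN. Its instructions include "Interrupt study treatment and repeat ECHO within 2 weeks" and "Report as an AE". The symptomatic rows (Grade 3: resting LVEF of 39 to 20%, or an absolute reduction of more than 20%; Grade 4: below 20%) call for permanent discontinuation and "Report as a SAE".

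Section 11.2, item h, lists protocol-specific SAEs. One entry begins "LVEF that meets the dose interruption criteria (Section 8.1.1.2" and goes on to spell out the threshold: an absolute, not relative, fall of more than 10% from baseline to a value below the LLN. It does not mention symptoms.

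Two later steps depend on the class. Under Section 11.12, once an event meets the SAE definition, "the SAE will be reported to the sponsor within 24 hours". SAP 2.7.1 plans registry tables that separate SAEs from "adverse events which are not serious adverse events with an incidence of at least 5" per cent.

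**The concern.** Both places are current protocol text, and they give opposite instructions for the same finding on an echocardiogram (ECHO). An asymptomatic fall will usually meet none of the general seriousness criteria in Section 11.2 (death, threat to life, hospitalization and so on), so item h alone normally decides its class. A site working from Table 13 would record an AE. A site working from Section 11.2h would record an SAE and report it within 24 hours.

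At stake are the speed at which the sponsor formally hears of a cardiac event of special interest, and whether the SAE and non-serious AE counts mean the same thing at every site.

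**Working it through.** The core of the check is textual.

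| Component | Table 13, asymptomatic row | Section 11.2h entry |
|---|---|---|
| Size of fall | absolute, more than 10% from baseline | the same |
| Level reached | below institutional LLN | below LLN |
| Symptoms | absent | no condition |
| Action | treatment interrupted | refers to the interruption criteria of 8.1.1.2 |
| Class | AE | SAE |

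1. The thresholds agree on both parts. The asymptomatic row is the only one in Table 13 that interrupts treatment; the symptomatic rows stop it permanently. The cross-reference in item h therefore lands on the row marked AE.

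2. Other item h events. Where Section 8 states a class for another listed event, it says SAE: cutaneous squamous cell carcinoma (8.2.2.1), new primary melanoma (8.2.2.2), non-cutaneous malignancy (8.2.2.3), combined ALT with bilirubin or INR elevations (Tables 15 and 16), and retinal pigment epithelial detachment or retinal vein occlusion (Table 25). Section 8.2.3 on pyrexia gives no class. The asymptomatic LVEF fall is the only listed event that Section 8 labels AE.

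3. A group that Table 13 omits. Take a hypothetical symptomatic fall from 60% to 45% where the LLN is 50%. The fall is 60 − 45 = 15 points and the value is below LLN, so it meets the numeric threshold in item h. It is not asymptomatic, 45% is above 39%, and 15 is not more than 20, so it fits no row of Table 13. Whether item h covers it depends on whether that entry is read through its cross-reference (the interrupting row only) or through its numeric threshold. Symptomatic Grade 3 or 4 falls are SAEs under Table 13 on either reading.

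4. Size, as an illustration only. The documents give no count of these events in this trial. Protocol 1.4 says that in two Phase III studies (melanoma) "decreased ejection fraction occurred in 7% of subjects receiving combination therapy". Assume that this rate carries over and that all 206 enrolled subjects were treated:

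- 0.07 × 206 = 14.4, about 14 subjects (14/206 = 6.8%).

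The 7% covers any decreased ejection fraction, so 14 is an upper bound for the disputed group and 0 is the lower bound. Protocol 1.4 adds that most falls meeting interruption criteria in those studies were asymptomatic, but not how many falls met those criteria, so the range cannot be narrowed.

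5. Could the label change a display? With 206 treated, the 5% cut-off is 0.05 × 206 = 10.3, so 11 subjects are needed. At the upper bound, and only if all 14 events shared one preferred term, labelling four of them SAE would leave 10 (10/206 = 4.9%), and the term would drop out of the non-serious table. This shows that mixed labelling could alter a table, not that it did.

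**The case against.** The best defence is that Section 11 governs seriousness. The opening of Section 11 refers sites to its definitions, Section 11.3 says abnormal safety assessments are to be recorded as AE or SAE according to those definitions, and Section 11.12 ties the 24-hour report to the protocol's SAE definition. Table 13 is a dose-modification table, and every SAE is also an AE, so its instruction need not exclude an SAE report.

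This narrows the ambiguity but does not remove it. No statement of precedence was found, and Table 13 sets the two instructions against each other row by row, which makes the reading that an AE may also be an SAE hard to sustain. The revision chronology does not settle it: under Amendment 5 it records changes both to SAE reporting in the LVEF criteria and to the list of protocol-specific SAEs.

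The second defence is that little depends on the label, and most of this stands. The sponsor collects copies of all ECHOs. Table 13 requires consultation with the Medical Lead. Section 11.3 requires an AE or SAE record for any safety assessment that led to interruption. Several SAP outputs do not use seriousness: all AEs by maximum grade, AEs leading to dose interruptions, and cardiac events of special interest. SAP 4.9 also defines an LVEF category for an absolute fall of 10 or more to below LLN. It comes from ECHO values and is almost the disputed event.

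A reader might infer that cardiac events went unrecorded or that the sponsor did not learn of them. The documents do not support that, given these safeguards.

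**Conclusion.** The contradiction is real and should be corrected, but its reach is short. It affects the 24-hour report and the SAE and non-serious AE displays of SAP 2.7.1. It does not affect any efficacy result or any safety output built without regard to seriousness.

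The number of events is unknown. The figure of about 14 is a ceiling that rests on three assumptions: that a rate from melanoma studies applies here, that all 206 subjects were treated, and that every such event was asymptomatic and met the interruption criteria. A reader might take it as 14 misclassified events; the documents do not show even one. Differing practice between sites is a fair inference from the conflicting text, not something the documents report. Nor do they establish that either section is the mistaken one.

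**What to change.** **Wording.** Reconcile Table 13 and Section 11.2h so that this event has one reporting class. State the class for symptomatic falls of more than 10% to below LLN that do not reach the Grade 3 or 4 rows. Tell sites. The choice of class is the sponsor's.

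**Events already recorded.**

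1. Start from the SAP 4.9 category (fall of 10 or more and below LLN), restrict it to falls of more than 10, and include unscheduled ECHOs.
2. Match by subject and date to AE records.
3. Cross-tabulate by presentation (asymptomatic; symptomatic below Grade 3; symptomatic Grade 3 or 4) and by recorded label (SAE; AE; not recorded).
4. Footnote the SAE and non-serious AE tables of SAP 2.7.1 with the first two groups. Keep the third apart, since Table 13 already makes it an SAE.

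The documents do not say whether symptom status is a recorded field. If it is not, derive it by medical review of concurrent AE terms, using the symptoms in footnote 2 of Table 13.

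**Cost.** A change to protocol wording, a site letter, and modest matching work with a short medical review of data already collected. The letter reaches only later events: enrollment ended on 29-Jun-2018, and 55 of 206 subjects were still on treatment on 06-Apr-2020. The cross-tabulation covers the rest.

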8.1.1.3 Hypertension

Increases in BP have been observed in subjects receiving trametinib. Recommendations for blood pressure monitoring and management are provided in Section 8.1.1.3.1 and Section 8.1.1.3.2, respectively.

8.1.1.3.1 Monitoring of Hypertension

All BP assessments should be performed under optimal conditions:

- the subject is seated in a semi-supine position with back support, ensuring that legs are uncrossed and flat on the floor
- the subject sits relaxed comfortably for at least 5 minutes
- restrictive clothing is removed from the cuff area and the right cuff size is selected
- the subject’s arm is supported so that the middle of the cuff is at the heart level
- the subject remains quiet during the measurement

Three readings of BP and pulse rate should be taken. The first reading should be rejected and the second and third readings averaged to give the measurement to be recorded in the eCRF.

Persistent hypertension is defined as an increase of systolic blood pressure (SBP) >140 mmHg and/or diastolic blood pressure (DBP) >90 mmHg in 3 consecutive visits with BP assessments from the readings collected as described above. Visits to monitor increased BP should be scheduled independently from the per-protocol visits outlined in the Time and Events Table (Section 7.1). Ideally, subsequent BP assessments should be performed within 7 days.

Asymptomatic hypertension is defined as an increase of SBP >140 mmHg and/or DBP >90 mmHg in the absence of headache, lightheadedness, vertigo, tinnitus, episodes of fainting or other symptoms indicative of hypertension.

8.1.1.3.2 Management of Hypertension

For subjects experiencing an increase in systolic and/or diastolic BP that is persistent and may be associated with the study treatment, recommendations for the clinical management of hypertension are described in Table 14.

Table 14 Management and Dose Modification Guidelines for Hypertension

Hypertension	Action and Dose Modification
(A). Asymptomatic and persistent ¹ SBP of ≥140 mmHg and <160 mmHg, or DBP ≥90 mmHg and <100 mmHg, or a clinically significant increase in DBP of 20 mmHg (but still <100 mmHg).	
 Continue study treatments at the current dose Adjust current or initiate new antihypertensive medication(s) Titrate antihypertensive medication(s) during the next 2 weeks as indicated to achieve well-controlled² BP If BP is not well controlled within 2 weeks, consider referral to a specialist and go to scenario (B).
(B). Asymptomatic SBP ≥160 mmHg, or DBP ≥100 mmHg, or failure to achieve well-controlled BP within 2 weeks in scenario (A).	
 Interrupt study treatments if clinically indicated Adjust current or initiate new antihypertensive medication(s) Titrate antihypertensive medication(s) during the next 2 weeks as indicated to achieve well-controlled BP Once BP is well controlled², restart study treatments reduced by one dose level³
(C). Symptomatic ⁴ hypertension or persistent SBP ≥160 mmHg, or DBP ≥100 mmHg, despite antihypertensive medication(s) and dose reduction of study treatment	
 Interrupt study treatments Adjust current or initiate new antihypertensive medication(s) Titrate antihypertensive medication(s) during the next 2 weeks as indicated to achieve well-controlled BP Referral to a specialist for further evaluation and follow-up is recommended Once BP is well controlled², restart study treatments reduced by one dose level³
Hypertension	Action and Dose Modification
(D). Refractory hypertension unresponsive to above interventions or hypertensive crisis	
 Permanently discontinue study treatments Continue follow-up per protocol.

Abbreviations: BP, blood pressure; DBP, diastolic blood pressure; mmHg, millimeters of mercury; SBP, systolic blood pressure

- Hypertension detected in 2 separate readings during up to 3 consecutive visits
- Well-controlled BP defined as SBP ≤140 mmHg and DBP ≤90 mmHg in 2 separate readings during up to 3 consecutive visits
- Escalation to previous dose level can be considered if BP remains well-controlled for 4 weeks after restarting. Approval from the Medical Lead is required.

4. Symptomatic hypertension defined as hypertension aggravated by symptoms (e.g. headache, lightheadedness, vertigo, tinnitus, episodes of fainting) that resolve after the BP is controlled within the normal range.

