 10. **BRIEF PHYSICAL EXAM:** A brief physical exam will be performed on Day 1 (if more than 72 hrs since the complete physical exam was performed for Screening) and every 4 weeks while on study treatment.
 11. **HEIGHT:** Height will be measured as part of complete physical exam performed at Screening only.
 12. **FULL DERMATOLOGICAL EXAM:** A full dermatological exam will be performed at Screening (or within 35 days prior to the first dose) only. A biopsy in and/or around a new skin lesion(s) or a lesion(s) that changes during the study is required if clinically indicated (refer to Section 7.4.2).
 13. **BRIEF DERMATOLOGICAL EXAM:** A brief dermatological exam will be performed every 4 weeks thereafter unless otherwise required to be performed more frequently. A brief dermatological exam should be performed every 4 weeks (± 7 days) for the first 6 months after discontinuation of study treatments. A biopsy in and/or around a new skin lesion(s) or a lesion(s) that changes during the study is required if clinically indicated (refer to Section 7.4.2).
 14. **OPHTHALMIC EXAM:** Ophthalmic exams will be performed at Screening (or within 35 days prior to the first dose), Week 4, and as clinically indicated thereafter.
 15. **VITAL SIGNS:** *Vital signs* include systolic/diastolic BP, temperature, pulse rate and respiratory rate. Vital signs should be measured in a semi-supine position after a 5 minute rest. *Blood pressure:* Three readings of BP and pulse rate should be taken. The first reading should be rejected and the second and third readings averaged to give the measurement to be recorded in the eCRF. If persistent hypertension (see Section 8.1.1.3.1) is noted in 3 consecutive visits, clinic visits to monitor the increased BP should be scheduled independently from the per-protocol visits. Ideally, subsequent BP assessments should be performed within 7 days of initial finding.
 16. **ECG:** A single 12-lead ECG should be performed after vital signs and before blood draws if assessments are planned at the same nominal time point. If clinically significant abnormality(ies) are seen, confirm with 2 additional ECGs taken at least 5 minutes apart. See Section 7.4.6 and SPM for additional information on ECG collection.
 17. **ECHO:** ECHOs will be performed at Screening (or within 35 days prior to the first dose), Week 4, Week 12, and then every 12 weeks thereafter. See Section 7.4.7 and SPM for additional information on ECHO collection.
- [REDACTED]

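### Persistent hypertension has two conflicting definitions (Protocol Section 8.1.1.3.1 and Table 14), and Table 14's entry and well-controlled ranges overlap at 140/90 mmHg

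*Protocol*

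**What the plan says.** Three places in the current protocol text bear on this.

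- **Section 8.1.1.3.1 (Monitoring of Hypertension):** "Persistent hypertension is defined as an increase of systolic blood pressure (SBP) >140 mmHg and/or diastolic blood pressure (DBP) >90 mmHg in 3 consecutive visits". It schedules extra visits for raised blood pressure, ideally at 7 days, and sets no earlier condition for them.
- **Section 8.1.1.3.2, Table 14:** row A covers asymptomatic, persistent "SBP of ≥140 mmHg and <160 mmHg, or DBP ≥90 mmHg and <100 mmHg". It also admits a clinically significant DBP rise of 20 mmHg. Note 1, attached to the word persistent in row A, reads "Hypertension detected in 2 separate readings during up to 3 consecutive visits". Note 2 reads "Well-controlled BP defined as SBP ≤140 mmHg and DBP ≤90 mmHg in 2 separate readings during up to 3 consecutive visits". The sentence that introduces the table limits it to increases that are persistent and may be related to study treatment.
- **Section 7.1, Time and Event Table, footnote 15:** "If persistent hypertension (see Section 8.1.1.3.1) is noted in 3 consecutive visits, clinic visits to monitor the increased BP should be scheduled independently". It then says: "Ideally, subsequent BP assessments should be performed within 7 days of initial finding". The event from which those 7 days run is not defined.

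Vital signs on treatment are scheduled every 4 weeks (±3 days). Each visit takes three readings; the first is discarded and the other two are averaged.

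**The concern.** Persistent is the word that opens Table 14. In row A it starts antihypertensive adjustment and a 2-week clock; failure to reach control within it moves the subject to row B, where interruption and restart at a lower dose level are possible. One limb of row C also depends on persistence, and carries no note saying which definition applies. Well controlled is the test for restart in rows B and C and, under note 3, for re-escalation.

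If the entry rule depends on which section a site reads, and the entry and exit ranges share values, the same readings can lead to different timing of management, interruption and restart. The SAP summarises dose interruptions and reductions (Section 2.3.3) and the AEs that lead to them (Section 2.7.1), so part of what is tabulated could reflect which passage a site followed.

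**Working it through.** There is no planned figure to reproduce. The check compares the passages and counts days.

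**1. The two definitions side by side**

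| | Section 8.1.1.3.1 | Table 14, row A with note 1 |
|---|---|---|
| Count | 3 of 3 consecutive visits | 2 readings within up to 3 consecutive visits |
| SBP | > 140 | ≥ 140 (and < 160) |
| DBP | > 90 | ≥ 90 (and < 100) |
| May readings share a visit? | No, it counts visits | Not stated |

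Two test cases, with DBP below 90 throughout:
- SBP 150, 135, 150 at three visits: persistent under Table 14 (two readings), not under 8.1.1.3.1 (the middle visit breaks the run).
- SBP exactly 140 at three visits: persistent under Table 14, not under 8.1.1.3.1 (140 is not above 140).

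Two readings remain at each visit after the first is discarded, so a literal reader could meet note 1 at a single visit.

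**2. Overlap inside Table 14**

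Row A needs SBP ≥ 140 or DBP ≥ 90. Note 2 needs SBP ≤ 140 and DBP ≤ 90. Both hold when SBP = 140 with DBP ≤ 90, or DBP = 90 with SBP ≤ 140. Two readings of 140/90 therefore satisfy entry and control together, and both notes use the same count of two readings.

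**3. Days from the first high visit until persistence is met**

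With k visits needed and a gap of g days between visits, days = (k − 1) × g. The ±3-day window on the first and last visit adds ±6 days on the 4-weekly schedule.

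| Visit spacing | 8.1.1.3.1, k = 3 | Table 14, k = 2 separate visits | Difference |
|---|---|---|---|
| 4-weekly, g = 28 | 2 × 28 = 56 (50 to 62) | 1 × 28 = 28 (22 to 34) | 28 |
| 7-day rechecks, g = 7 | 2 × 7 = 14 | 1 × 7 = 7 | 7 |

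If two readings at one visit count, Table 14 gives 0 days on either schedule.

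**4. Illustration of the difference in count**

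Assume, for illustration only, that visits are independent, each is high with chance p, and there is one reading per visit. Three of three has probability p³; at least two of three has p³ + 3p²(1 − p).
- p = 0.3: 0.027 versus 0.216
- p = 0.5: 0.125 versus 0.500
- p = 0.7: 0.343 versus 0.784
- p = 0.9: 0.729 versus 0.972

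Real readings within a subject are correlated, so these show direction, not an expected rate.

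**5. Footnote 15**

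Read literally, the extra visits begin only after three consecutive high visits. If the 7 days run from the first high visit, that mark has passed by then: 7 days against 56 on the 4-weekly schedule. If they run from the point at which persistence is recognised, the footnote agrees with itself but still differs from Section 8.1.1.3.1, which sets no three-visit precondition for extra visits.

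**The case against.** Several points on the other side stand.

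- A reader might infer three definitions. The documents do not support that: footnote 15 refers to Section 8.1.1.3.1 and repeats its three-visit count. It is a scheduling rule that differs from that section, not a third definition.
- A reader might infer an eightfold spread, from 56 days against 7 (56 / 7 = 8). That pairs one definition with 4-weekly visits and the other with 7-day rechecks. On the same spacing, with separate visits, the ratio is two (56 / 28 or 14 / 7).
- A reader might infer that footnote 15 forces confirmatory visits to come after the state they should confirm. Both passages give the purpose of the extra visits as monitoring, and the start of the 7-day interval is left open. The footnote is ambiguous, not plainly contradictory. The 56-day case also needs a site to disregard the 7-day recheck in Section 8.1.1.3.1 and the allowance in Section 7.4.4 for more frequent vital signs.
- Table 14 is presented as recommendations. Row A keeps the dose unchanged, and interruption in row B is only if clinically indicated. Row B as worded does not require persistence, although the sentence introducing the table does.
- A reader might infer distortion of the hypertension AE of special interest. SAP Section 2.7.1.1 identifies those events by MedDRA terms, with no persistence criterion, so any effect is indirect and not shown.
- Response is not affected, and with a single arm there is no between-arm comparison to bias. Enrollment closed on 29-Jun-2018.

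Against this, Section 4 requires adherence to the Time and Events Table, so a literal reading of footnote 15 is reasonable. Amendment 11 records 55 subjects still on treatment at 06-Apr-2020. None of these points removes the conflict in count and inequality or the overlap at 140/90.

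**Conclusion.** The protocol contradicts itself on when hypertension is persistent, in both the count and the inequality, and Table 14's entry and well-controlled ranges share 140 and 90. These two findings rest on the text alone.

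The size depends on visit spacing: 28 days' difference on 4-weekly visits, 7 days with 7-day rechecks, and up to 56 or 14 days respectively if Table 14 can be met at one visit. These figures assume the subject is high at every visit from the first.

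The effect falls on entry to row A and its 2-week clock to row B, on the persistent limb of row C, and on the well-controlled test for restart and re-escalation. The documents give no basis for estimating how many interruptions or reductions would change. Footnote 15 adds ambiguity about when extra visits start. This is an internal inconsistency that should be corrected; it does not threaten the primary endpoint.

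**What to change.** Reconcile Time and Event footnote 15, Section 8.1.1.3.1, and Table 14 row A with notes 1 and 2, so that they agree on:

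- the number of readings and the number of visits that make hypertension persistent;
- whether two readings may come from the same visit;
- the inequality at the threshold (strict or inclusive);
- the values 140 and 90, which at present fall in both the row A and well-controlled ranges;
- what starts the extra blood-pressure visits, and from which date the 7-day interval runs.

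Also state which meaning of persistent applies to row C and to the sentence introducing Table 14. The choice of rule belongs to the sponsor; none is proposed here.

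The cost is wording in one schedule footnote, one paragraph and a few lines of Table 14 and its notes. Whether the number of visits changes depends on the rule chosen.
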